## **2. TYPE OF PLANNED ANALYSIS**

### **2.1. Interim Analysis**

A single formal interim analysis is planned under Simon's optimal 2-stage design. The sole purpose of this interim analysis is to determine if there is a sufficient ORR observed early in the study to warrant continuing the study to completion. The interim analysis constitutes a futility analysis; it will not be used to stop the trial early for positive efficacy.

In Stage 1 of the study, 31 subjects will be enrolled. If  $\geq 9$  Stage 1 subjects have a response (ie, complete response or partial response), then the study will continue. If  $< 9$  Stage 1 subjects have a response, accrual to the study will be halted. At the end of Stage 1, the probability of erroneously proceeding with the study is 0.151 under the null hypothesis and of erroneously discontinuing the study is 0.091 under the alternative hypothesis.

If the required Stage 1 tumor ORR is seen based on investigator assessments, accrual can proceed in Stage 2 without interruption. If the required total number of subjects are accrued to Stage 1 but follow-up is not sufficiently mature (ie, through the Week 16 radiographic evaluation) in all Stage 1 subjects to reasonably assess the Stage 1 ORR, accrual to Stage 2 may proceed while the Stage 1 data are being collated. All available tumor response and progression data will be considered at the time of the assessment. At the latest, the interim analysis will be performed when the last of the Stage 1 subjects has been enrolled and has completed the 16-week tumor assessment and these data are evaluated.

### **2.2. Final Analysis**

In Stage 2 of the study, it is planned that 69 subjects will be enrolled to achieve the total intended sample size of 100 subjects. The final study analysis will be performed when all enrolled subjects have completed efficacy, safety, and other assessments through at least 24 weeks of evaluation.

### **3. GENERAL CONSIDERATIONS FOR DATA ANALYSES**

#### **3.1. Analysis Sets**

##### **3.1.1. Intent-to-Treat Analysis Set**

The intent-to-treat (ITT) analysis set will comprise all subjects who receive  $\geq 1$  dose of IDELA. The ITT analysis set will be used in the analyses of ORR, progression-free survival (PFS), overall survival (OS), safety, and study drug administration and compliance. The ITT analysis set will be the primary analysis set for all the efficacy variables.

Duration of response (DOR) and time-to-response (TTR) will be analyzed based on all ITT subjects who achieve a CR or PR (including MR for subjects with WM). Lymph node response rate (LNR) will be analyzed based on all ITT subjects who have both baseline and  $\geq 1$  evaluable post-baseline tumor assessments.

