### 1.3. Sample Size and Power

Planned Sample Size	Up to 120 subjects may be enrolled in order to ensure enrollment of $\geq$ 100 subjects (31 in Stage 1, and 69 in Stage 2) who have a documented diagnosis of lymphoma, who have confirmed refractory disease, and who can be evaluated for tumor response with baseline and on-study scans (through the planned 24-week, follow-up tumor assessment).
Power Statement	The null hypothesis that the IRC-reviewed ORR is $\leq$ 20% will be tested against the alternative hypothesis that it is $\geq$ 39% (ie, $\sim$ 40%). Using Simon's optimal 2-stage design [Simon 1989], a sample size of 100 subjects has power $>$ 0.90 to achieve a 1-sided significance level of $<$ 0.005 and will provide an adequate safety database.
Actual Enrollment and Impact on Power	A total of 125 subjects have been enrolled into this study and this will provide $>$ 0.90 power to test the primary hypothesis.

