##### **3.1.2. Per Protocol Analysis Set**

It is anticipated that ITT subjects who meet any of the following criteria will not be included in the per protocol (PP) analysis set:

- Do not have a diagnosis of lymphoma or documented refractory disease (refractory to both rituximab and an alkylating agent)
- Do not have measurable nodal disease at baseline as determined by the IRC
- Do not have a PFS event (PD or death), and do not have baseline and on-study tumor evaluation.

The PP analysis set will be used in analyses of ORR, DOR, TTR, LNR and PFS.

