### 6.1. Definition of the Primary Efficacy Endpoint

A best overall response of CR, PR, stable disease (SD), PD, not evaluable (NE) and no disease (ND) is allowed. For subjects with WM, a minor response (MR) is also allowed. In the event that a single PD is followed by an assessment that is SD, PR or CR which is the same or better than the prior nadir response and there is substantial interruption of exposure to study drug, that PD may not be considered in the BOR evaluation in accordance with the Gilead Protocol 101-09 Imaging Charter.

ORR is defined as the proportion of subjects who achieve a CR or PR (or MR for subjects with WM) during the IDELA treatment. The response definitions for each category are based on standard criteria and defined in Section 8.1.5 of the protocol. Subjects who do not have sufficient baseline or on-study tumor status information to be adequately assessed for response status (ie, those with best overall responses of NE or ND) will be included in the denominators in calculations of response rates.

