### **6.4. Secondary Efficacy Endpoints**

#### **6.4.1. Definition of Secondary Efficacy Endpoints**

- DOR – defined as the interval from the first documentation of CR or PR (or MR for WM subjects) to the earlier of the first documentation of disease progression or death from any cause
- LNR – defined as the proportion of subjects who achieve a  $\geq 50\%$  decrease from baseline in the SPD
- TTR – defined as the interval from the start of study drug to the first documentation of CR or PR (or MR for WM subjects)
- PFS – defined as the interval from the start of study drug to the earlier of the first documentation of disease progression or death from any cause
- OS - defined as the interval from the date of first IDELA to death from any cause
- Changes in HRQL as reported by subjects using the FACT-Lym
- Changes in performance status as documented using the Karnofsky performance criteria

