##### **6.4.2.2. Lymph Node Response Rate**

The LNR will be summarized with 95% CI using the exact method based on the ITT and PP analysis sets using both the IRC assessments and investigators assessments.

The SPD and percent change in SPD from baseline to each subsequent assessment will be summarized using both the IRC assessments and investigators assessments. The best percent change from baseline during the study will also be summarized based on the first reader of each reader pair ([Gilead Protocol 101-09 Imaging Charter]) unless the adjudicator choose the second reader. The best percent change from baseline in SPD is defined as the largest decrease in tumor size while the subject was on-treatment. The baseline SPD will be the last value prior to the start of IDELA therapy. Note that for subjects who only have increases in tumor size from baseline, the smallest increase will be considered as the best change from baseline in SPD. Analyses will be conducted for the ITT and PP analysis sets.

A waterfall plot of best on-treatment percent change in SPD based on the IRC and investigators assessments will be provided. Individual records for measurable and nonmeasurable lesions will be listed in detail.

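### Lymph node response rate drops treated subjects who have no evaluable post-baseline scan, so a rate labelled ITT can only be equal to or higher than the rate that counts them as non-responders

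*SAP*

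**What the plan says.** Section 3.1.1 defines ITT as all subjects who took at least one dose and says that "The ITT analysis set will be the primary analysis set for all the efficacy variables". It then sets a narrower population for this endpoint: "Lymph node response rate (LNR) will be analyzed based on all ITT subjects who have both baseline and" at least one of the "evaluable post-baseline tumor assessments".

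The other relevant text is:

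- Section 6.4.1 defines the endpoint ("LNR – defined as the proportion of subjects who achieve a" fall of 50% or more in SPD from baseline) and gives no denominator rule.
- Section 6.4.2.2 gives the analysis: "The LNR will be summarized with 95% CI using the exact method based on the ITT and PP analysis sets". It does not repeat the evaluability condition and has no non-responder rule.
- Section 3.7 makes the full analysis set the default denominator unless something else is specified. Section 3.6 rules out imputation unless a method is given. None is given for LNR.
- Section 6.1, for ORR, says that subjects with too little baseline or on-study tumor information "will be included in the denominators in calculations of response rates".
- Section 3.1.2 removes from the per-protocol (PP) set those who "Do not have a PFS event (PD or death), and do not have baseline and on-study tumor evaluation".

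**The concern.** Whether a subject has an evaluable post-baseline scan is settled after treatment begins. Section 6 places the first scheduled on-study scan at Week 8. A subject who dies, deteriorates or withdraws before any evaluable scan therefore leaves the LNR denominator because of something that happened on treatment. For ORR the same subject counts as a non-responder.

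The reported LNR would then describe only subjects who reached an evaluable scan, while Tables 2.2.1 and 2.2.2 carry the label ITT Analysis Set. A reader would take the percentage as the rate among treated subjects. Part of any gap between LNR and ORR would come from the denominators and not from the tumor measurements.

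There is also a question about the PP set. The evaluability condition is written for ITT subjects only. Under section 3.1.2, a subject without an on-study evaluation leaves PP only if there is also no PFS event, so that criterion keeps an early death without a scan. Read literally, LNR on PP could count a failure that LNR on ITT drops.

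**Working it through.** The SAP states no expected LNR and no number of subjects without a scan, so there is no planned figure to reproduce. The check has two parts: which rule governs, and what it does to the rate.

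**Which rule governs.** Section 3.7 gives way to a specific rule, and section 3.1.1 is one. Sections 3.6 and 6.4.2.2 supply nothing that would bring unscanned subjects back as non-responders. The plural used in section 6.1 could be stretched to cover LNR, but the sentence sits under the ORR definition, so section 3.1.1 is the operative text.

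**Direction.** Let N be the treated subjects with a baseline SPD, m those among them with no evaluable post-baseline scan, and x the lymph node responders. None of the m subjects can be in x, because a fall in SPD needs a post-baseline SPD.

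- SAP rule: x/(N−m)
- Unscanned counted as non-responders: x/N
- Ratio: N/(N−m), which is at least 1. The two rates are equal only if m = 0 or x = 0.

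**Inputs for the size.**

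- N = 125, the enrolment reported in section 1.3. This assumes that all were dosed and had a baseline SPD.
- m is not given. The only related figure is the allowance in section 1.3 of up to 120 enrolled to secure 100 subjects "who can be evaluated for tumor response with baseline and on-study scans", that is 20/120 = 16.7%. That allowance also covers unconfirmed diagnosis and unconfirmed refractoriness, and the end-of-treatment scan in section 6 should keep m/N below it. Assumed values: m = 6, 12 and 19 (4.8%, 9.6% and 15.2% of 125).
- x is not given. Assumed values: 50, 63 and 75.

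**Result for x = 63** (exact Clopper-Pearson 95% intervals):

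| m dropped | Denominator | LNR | 95% CI | N/(N−m) |
|---|---|---|---|---|
| 0 | 125 | 50.4% | 41.3–59.5 | 1.000 |
| 6 | 119 | 52.9% | 43.6–62.2 | 1.050 |
| 12 | 113 | 55.8% | 46.1–65.1 | 1.106 |
| 19 | 106 | 59.4% | 49.5–68.9 | 1.179 |

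**Other response levels**, for m = 0, 6, 12 and 19:

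- x = 50: 40.0%, 42.0%, 44.2%, 47.2%
- x = 75: 60.0%, 63.0%, 66.4%, 70.8%

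**If few scans are missing**, for example m = 3 (denominator 122):

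- 50/122 = 41.0%, against 40.0%
- 75/122 = 61.5%, against 60.0%

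**The case against.** The strongest reply is that this is a pre-specified choice and not an error. Section 3.1.1 states the population openly, section 3.7 allows it, and a change in SPD cannot be computed without a post-baseline SPD. LNR has no hypothesis, threshold or multiplicity role, and the conservative measure in all treated subjects already exists as the primary ORR. All of this is true. It limits the consequence, but it does not change the direction of the effect or the mismatch between the table label and the denominator.

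The size is assumed. Section 6 asks for an end-of-treatment scan when a subject leaves for reasons other than progression on routine imaging and the last scan is more than 4 weeks old. That should recover many early withdrawals, and nothing in the SAP supports 10% or 15% missing. With 6 subjects missing, the shift is 2.5 points (50.4% to 52.9%) against an interval about 18 points wide (41.3 to 59.5). This stands: the effect may be small.

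The PP point is the weakest part. Every PP subject is an ITT subject, so the likelier reading is that the section 3.1.1 condition carries over. Section 6.4.2.2 does not say so, and the appendix lists no LNR table for PP that would settle it. It needs one clarifying sentence.

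Finally, the tabulated NE and ND counts (section 6.3) and the N and n in the SPD summaries (section 3.7) give a rough view of who is missing. Also, a denominator that requires a baseline SPD still differs from the ORR denominator. Both points are fair. The difference that would remain rests on a pre-treatment condition, which does not select on outcome.

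**Conclusion.** The concern holds. As written, LNR is conditioned on a post-treatment event and cannot be lower than the rate with unscanned subjects counted as non-responders. That direction follows from arithmetic. The size depends on the number without an evaluable scan, which the SAP does not give. For true rates of 40% to 60% and N = 125, the excess is about 1 to 1.5 points with 3 subjects missing, 2 to 3 points with 6, 4 to 6 points with 12, and 7 to 11 points with 19. The larger values are illustrations and not expectations.

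Section 3.1.1 is a stated exception, so it does not breach section 6.1. No decision rule is affected, because LNR is a secondary, descriptive endpoint. The change is worth making because it is cheap and removes a selectively favourable figure from a table labelled ITT.

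**What to change.** - In sections 3.1.1 and 6.4.2.2, make the main LNR denominator all ITT subjects with a measurable baseline SPD. Count those without an evaluable post-baseline scan as non-responders.
- State that the same rule applies to LNR on the PP set.
- Report how many ITT subjects are left out for lack of a baseline SPD.
- Keep the evaluable-only rate as a labelled sensitivity analysis, with the number excluded shown in a footnote to Tables 2.2.1 and 2.2.2.

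The cost is SAP wording and one extra row or footnote in the LNR tables. No new data are needed. The reported LNR will be slightly less favourable if any subject lacks an evaluable scan.

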##### **3.1.2. Per Protocol Analysis Set**

It is anticipated that ITT subjects who meet any of the following criteria will not be included in the per protocol (PP) analysis set:

- Do not have a diagnosis of lymphoma or documented refractory disease (refractory to both rituximab and an alkylating agent)
- Do not have measurable nodal disease at baseline as determined by the IRC
- Do not have a PFS event (PD or death), and do not have baseline and on-study tumor evaluation.

The PP analysis set will be used in analyses of ORR, DOR, TTR, LNR and PFS.

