	

• Age <math>\geq</math> 18 years

• Karnofsky performance score <math>\geq</math> 60 (Eastern Cooperative Oncology Group [ECOG] performance score of 0, 1, or 2)

• Histologically confirmed diagnosis of B-cell iNHL, with histological subtype limited to the following based on criteria established by the World Health Organization (WHO) 2008 classification of tumors of haematopoietic and lymphoid tissues:

— Follicular lymphoma (FL) Grade 1, 2, or 3a

— Small lymphocytic lymphoma (SLL) with absolute lymphocyte count <math><5 \times 10^9/L</math> at the time of diagnosis and on baseline laboratory assessment performed within 4 weeks prior to the start of study drug administration

— Lymphoplasmacytic lymphoma/Waldenstrom Macroglobulinemia (LPL/WM)

— Marginal zone lymphoma (MZL) (splenic, nodal, or extra-nodal)

• Histological materials documenting diagnosis of lymphoma available for review. Note: Central pathology confirmation of diagnosis will be performed in this study. However, a subject may be enrolled without waiting for confirmation of histological diagnosis on condition that pathological materials are known to be available for review.

• Presence of radiographically measurable lymphadenopathy or extranodal lymphoid malignancy (defined as the presence of <math>\geq 1</math> lesion that measures <math>\geq 2.0</math> cm in the longest dimension [LD] and <math>\geq 1.0</math> cm in the longest perpendicular dimension [LPD] as assessed by <math>\geq</math> CT or magnetic resonance imaging [MRI])

• Prior treatment with <math>\geq 2</math> chemotherapy- or immunotherapy-based regimens, or with rituximab/with an alkylating agent for iNHL

• Prior treatment with rituximab and with an alkylating agent (eg, bendamustine, cyclophosphamide, ifosfamide, chlorambucil, melphalan, busulfan, nitrosoureas) for iNHL.

• Lymphoma that is refractory to rituximab and to an alkylating agent

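### The per-protocol histology exclusion asks only for a lymphoma diagnosis, so a subject reclassified to an ineligible lymphoma stays in the supportive per-protocol analyses

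*SAP*

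**What the plan says.** **Eligibility (Section 1.2, Key Eligibility Criteria).** Entry requires a "Histologically confirmed diagnosis of B-cell iNHL, with histological subtype limited to the following" list: FL Grade 1, 2 or 3a; SLL under a lymphocyte limit; LPL/WM; and MZL. Central pathology review is part of the study, but "a subject may be enrolled without waiting for confirmation of histological diagnosis" provided that material is known to be available.

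**Sample size (Section 1.3).** The 100 subjects the design needs are those "who have a documented diagnosis of lymphoma, who have confirmed refractory disease" and who can be evaluated for response. No subtype is named.

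**PP set (Section 3.1.2).** The list opens with "It is anticipated that ITT subjects who meet any of the following criteria will not be included". The first exclusion covers subjects who "Do not have a diagnosis of lymphoma or documented refractory disease (refractory to both rituximab and an alkylating agent". The other two cover those who "Do not have measurable nodal disease at baseline as determined by the IRC" and those who "Do not have a PFS event (PD or death), and do not have baseline and on-study tumor evaluation".

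**Use.** "The PP analysis set will be used in analyses of ORR, DOR, TTR, LNR and PFS". Section 3.1.1 makes ITT the primary set for every efficacy variable. Section 6.4.2.1 lists the PP analyses of DOR and PFS among the sensitivity analyses for robustness.

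**The concern.** The first PP exclusion contains two disease conditions. The refractoriness half follows the eligibility rule closely and names both drug classes. The histology half widens it from a short list of indolent subtypes to lymphoma of any kind. Follicular lymphoma above Grade 3a, or an aggressive lymphoma, is still a lymphoma. A subject found on central review to have one fails a central entry criterion and yet passes the PP test.

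The enrolment rule makes this possible, because treatment can begin before the central result is known. A PP analysis would normally show whether the results hold once such subjects are set aside. As written, it cannot show that for histology.

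**Working it through.** **Step 1. Trace one subject through the rules.** Take a subject enrolled on a local diagnosis of an eligible subtype. Central review later gives a lymphoma outside the Section 1.2 list.

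- ITT (Section 3.1.1): included, as at least one dose was taken. This is by design.
- PP exclusion 1, histology part: the subject has a lymphoma, so is not excluded.
- PP exclusion 1, refractoriness part: depends on treatment history, not subtype.
- PP exclusion 2: depends on measurable nodal disease as judged by the IRC, not subtype.
- PP exclusion 3: depends on tumor evaluation and PFS events, not subtype.

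No PP criterion mentions iNHL, an eligible subtype or the central pathology result, and no other section removes the subject. Section 1.3 uses the same broad term, so it does not narrow the rule.

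**Step 2. Does any stated figure depend on this?** No. The Stage 1 probabilities in Section 2.1 reproduce by exact binomial calculation: P(X ≥ 9 | 31, 0.20) = 0.1508 (stated 0.151) and P(X ≤ 8 | 31, 0.39) = 0.0908 (stated 0.091). Neither uses the PP definition.

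**Step 3. Size of the effect on PP ORR.** Let N be the PP size, m the number of retained ineligible subjects, p the ORR in eligible subjects and q the ORR in the retained subjects.

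PP ORR = ((N − m)p + mq) / N, so the shift from p is (m/N)(q − p).

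The inputs are N = 125 (actual enrolment, Section 1.3), N = 100 (planned size) and p = 39% (alternative hypothesis, Section 6.2). The SAP gives neither m nor q, so both are assumptions.

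With a 20-point gap and N = 125:
- m = 3: 3/125 = 0.024; 0.024 × 20 = 0.48, about 0.5 points.
- m = 10: 10/125 = 0.08; 0.08 × 20 = 1.6 points.

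Outer bounds, where none or all of the retained subjects respond:

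| N | m | None respond | All respond |
|---|---|---|---|
| 125 | 5 | 120 × 0.39 / 125 = 37.4% | (46.8 + 5) / 125 = 41.4% |
| 125 | 10 | 115 × 0.39 / 125 = 35.9% | (44.85 + 10) / 125 = 43.9% |
| 100 | 5 | 95 × 0.39 / 100 = 37.1% | (37.05 + 5) / 100 = 42.1% |
| 100 | 10 | 90 × 0.39 / 100 = 35.1% | (35.1 + 10) / 100 = 45.1% |

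For scale, the approximate 95% half-width at 39% is 1.96 × √(0.39 × 0.61 / N). That is 8.6 points at N = 125 and 9.6 points at N = 100. Even the outer bounds lie within one half-width of 39%.

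The SAP gives no basis for a similar calculation for DOR or PFS.

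**The case against.** **Lymphoma may be shorthand.** Section 1.2 itself uses the bare word where the trial disease is plainly meant, for example in the refractoriness criterion. The intent may well have been iNHL. That makes imprecise drafting more likely than a deliberate choice to keep other lymphomas. A programmer who applies the written rule would still keep the subject.

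**The list is provisional.** It is introduced as anticipated, so further exclusions could be added, and Section 4.4 has major protocol deviations summarised and listed. Ineligible histology could surface there, but Section 4.4 removes nobody from the PP set. In an open-label, single-arm trial it is better to fix the rule than to leave it for decision once responses are known.

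**Other analyses touch histology.** A reader might infer that the PP set is the only check of results in the eligible disease. The SAP does not support that. Section 3.4 plans ORR, DOR, TTR and PFS by FL, SLL, WM and MZL; only LNR is absent. This point stands, with limits: the SAP does not say whether subcategory follows central pathology, FL is not split by grade, and no category exists for another lymphoma.

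**Misclassification need not be common.** A reader might infer that it is expected, or the likeliest eligibility failure. The SAP says neither. A histologically confirmed diagnosis is required at entry, and only the central confirmation may come later.

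**Conclusion.** The point holds as a rule stated too widely. Under Section 3.1.2 as written, a subject reclassified to an ineligible lymphoma remains in the PP analyses unless an unrelated exclusion applies. The consequence is confined to those supportive analyses. The hypothesis test is in the ITT set (Section 6.3), and PP membership alters neither that test nor the Stage 1 decision, so a doubt about the primary conclusion does not follow.

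The size is unknown and probably small: about 0.5 to 1.6 points of PP ORR, assuming 3 to 10 reclassified subjects among 125 and a 20-point gap in ORR. That the PP set is meant to represent eligible iNHL is an inference from its name and the entry criteria, since the SAP does not state its purpose beyond robustness of DOR and PFS.

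**What to change.** In Section 3.1.2, replace the requirement for a lymphoma diagnosis with: *a diagnosis of an eligible iNHL subtype (Section 1.2), with central pathology review taking precedence where available and the local histological diagnosis used where central review is missing or inadequate*. The fallback matters because a rule requiring central confirmation would also drop subjects whose review was never completed.

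For SLL, apply the lymphocyte limit to the baseline laboratory value. The limit is a laboratory criterion that pathology review does not settle. Section 1.2 also applies it at diagnosis, but the SAP does not show that the count at diagnosis is collected.

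Use the same wording in Section 1.3, leave the ITT set unchanged, and make the change before the final analysis.

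The cost is SAP text and a small change to the derivation of the PP flag. Central review and baseline laboratory tests are already planned. The PP set may be slightly smaller.
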